7.2.22 Treatment

The following procedures will be completed during each cohort treatment period at the times designated in the Schedule of Assessments (Table 5.). Administration of AMG 224 is to be administered after all protocol-specific pre-dose assessments has been performed during each visit that it is required.

Clinical evaluation to include the following:

- Physical examination with neurological assessment and ECOG performance status
- Peripheral neuropathy assessment
- Vital signs (blood pressure, respiratory rate, heart rate, temperature)
- 12-lead ECG
 - collected after subject has rested for 5 minutes.
 - record QRS, QT, QTc, RR and PR intervals.

- Pregnancy test – serum or urine (only females of childbearing-potential)
- Safety Laboratory Assessments (locally tested)
 - Chemistry
 - Hematology
 - Coagulation
 - Urinalysis
- Blood collection
 - PK (DM1 & AMG 224 conjugated antibody and Total anti-BCMA antibody PK)
 - Anti-AMG 224 antibody
 - Biomarker
- Serum protein electrophoresis (SPEP) and 24-hour urine protein electrophoresis (UPEP)
- Serum free light chain (SFLC)
- Imaging Assessments (plasmacytoma and skeletal survey)
- Adverse event assessment is performed throughout the study at every visit
 - Serious adverse events are collected from the time the subject signs the ICF.
 - Adverse events are collected from the time the subject is dosed on day 1.
- Documentation of concomitant medications

7.2.23 End of Treatment

The end of treatment (EOT) visit will occur after the last dose of AMG 224. For subjects who choose to discontinue investigational product treatment, the EOT visit should occur as soon as possible after the last dose of investigational product is administered.

Serious adverse events considered related to the investigational product, by the Investigator, or Amgen will be followed until resolved or considered stable.

Clinical evaluation to include the following:

- Physical examination with neurological assessment and ECOG performance status
- Vital signs (blood pressure, respiratory rate, heart rate, temperature)
- Peripheral neuropathy assessment
- 12-lead ECG
 - collected after subject has rested for 5 minutes.
 - record QRS, QT, QTc, RR and PR intervals.
- Safety Laboratory Assessments (locally tested)
 - Chemistry
 - Hematology

- Coagulation
- Urinalysis
- Blood collection
 - Anti-AMG 224 antibody
 - Biomarker
- Serum protein electrophoresis (SPEP) and 24-hour urine protein electrophoresis (UPEP)
- Serum free light chain (SFLC)
- Adverse event assessment is preformed throughout the study at every visit
 - Serious adverse events are collected from the time the subject signs the ICF.
 - Adverse events are collected from the time the subject is dosed on day 1.
- Documentation of concomitant medications

7.2.24 End of Study Visit

The EOS visit must be performed 30 to 37 days after the last dose of AMG 224. All efforts should be made to conduct this visit. If it is not possible to conduct the EOS visit, documentation of efforts to complete the visit should be provided in the source documents and noted as not done in the eCRFs.

Clinical evaluation to include the following:

- Physical examination with neurological assessment and ECOG performance status
- Vital signs (blood pressure, respiratory rate, heart rate, temperature)
- Peripheral neuropathy assessment
- 12-lead ECG
 - collected after subject has rested for 5 minutes.
 - record QRS, QT, QTc, RR and PR intervals.
- Safety Laboratory Assessments (locally tested)
 - Chemistry
 - Hematology
 - Coagulation
 - Urinalysis
- Blood collection
 - Biomarker
 - Anti-AMG 224 antibody
- Serum protein electrophoresis (SPEP) and 24-hour urine protein electrophoresis (UPEP)
- Serum free light chain (SFLC)

Approved

- Adverse event assessment is performed throughout the study at every visit
 - Serious adverse events are collected from the time the subject signs the ICF.
 - Adverse events are collected from the time the subject is dosed on day 1.
- Documentation of concomitant medications

7.3 Antibody Testing Procedures

Blood samples for anti-drug antibody (ADA) testing are to be collected at the time points as specified in the table of assessment (Table 5.). Samples testing positive for binding anti-AMG 224 antibodies may be further characterized for quantity/titer, isotype, affinity and presence of immune complexes. Additional blood samples may be obtained to rule out anti-AMG 224 antibodies during the study. The incidence of binding anti-AMG 224 antibodies will be reported, and the impact of ADA on pharmacokinetics, pharmacodynamics, safety and efficacy will be evaluated.

Samples testing positive for binding anti-AMG 224 antibodies will be banked and may be analyzed in a validated in-vitro neutralizing assay during late-stage clinical development.

7.4 Biomarker Development

In addition to testing the safety and effectiveness of the experimental drug AMG 224 in this study, Amgen will attempt to develop tests from blood and/or tumor tissue that will identify subjects most likely to benefit from AMG 224. Biomarkers are objectively measured and evaluated indicators of normal biologic processes, pathogenic processes, or pharmacologic responses to a therapeutic intervention. In oncology, there is particular interest in the molecular changes underlying the oncogenic processes that may identify cancer subtypes, stage of disease, assess the amount of tumor growth, or predict disease progression, metastasis, and responses to AMG 224 or protocol required therapies.

Biomarker development may be pursued by use of advanced biochemical analyses, such as proteomic methods or ribonucleic acid transcript profiling. Some of the biomarkers to be explored include but are not limited to, BCMA and BCMA ligand expression, mutation status, analysis of BCMA RNA transcripts in tumors, enumeration and/or signaling activity of CTCs levels of soluble BCMA and BCMA ligands.

Blood Samples

Blood samples are to be collected for biomarker development at the time points as listed in the schedule of assessments. Plasma samples may also be used to explore whether

expression or mutation of specific commonly occurring mutations found in tumors tissues (and other genes based on emerging data) correlates with response to AMG 224.

7.5 Bone Marrow

During screening, bone marrow sample is required for all subjects. Samples will be sent to the central laboratory along with the corresponding pathology report. The tumor block is to be carefully selected by a pathologist or a skilled experienced histology associate to include generous tumor tissue using the Pathology Report as a guide. In lieu of a block, 20 unstained sections on charged slides from the same block can be submitted within 4 weeks of study day 1 to allow time to evaluate the samples, and to ask for additional samples if the initial samples are not appropriate. Analyses of tumor specific mutations or epigenetic changes may be performed (eg, somatic mutations) when the samples of tumor tissues become available. Minimal residual disease will be evaluated on the bone marrow specimen of the patients that achieve complete remission per IMWG.

7.6 Pharmacogenetic Studies

If the subject consents to the optional pharmacogenetic portion of this study, DNA analyses may be performed. These optional pharmacogenetic analyses focus on inherited genetic variations to evaluate their possible correlation to the disease and/or responsiveness to the therapies used in this study. The goals of the optional studies include the use of genetic markers to help in the investigation of multiple myeloma and/or to identify subjects who may have positive or negative response to AMG 224. No additional samples are collected for this part of the study however for subjects who consent to this/these analysis/analyses, DNA may be extracted from the blood samples collected for the biomarker studies will be used for this purpose.

7.7 Sample Storage and Destruction

Any remaining blood and tumor samples collected according to the Schedule of Assessments ([Table 5.](#)) can be analyzed for any of the tests outlined in the protocol and for any tests necessary to minimize risks to study subjects. This includes testing to ensure analytical methods produce reliable and valid data throughout the course of the study. This can also include, but is not limited to, investigation of unexpected results, incurred sample reanalysis, and analyses for method transfer and comparability.

All samples and associated results will be coded prior to being shipped from the site for analysis or storage. Samples will be tracked using a unique identifier that is assigned to the samples for the study. Results are stored in a secure database to ensure confidentiality.

If informed consent is provided by the subject, Amgen can do additional testing on remaining samples (ie, residual and back-up) to investigate and better understand the multiple myeloma, the dose response and/or prediction of response to AMG 224 and characterize aspects of the molecule (eg, mechanism of action/target, metabolites). Results from this analysis are to be documented and maintained but are not necessarily reported as part of this study. Samples can be retained for up to 20 years.

Since the evaluations are not expected to benefit the subject directly or to alter the treatment course, the results of pharmacogenetic, biomarker development, or other exploratory studies are not placed in the subject's medical record and are not to be made available to the subject, members of the family, the personal physician, or other third parties, except as specified in the informed consent.

The subject retains the right to request that the sample material be destroyed by contacting the investigator. Following the request from the subject, the Investigator is to provide Amgen with the required study and subject number so that any remaining blood or tumor samples and any other components from the cells can be located and destroyed. Samples will be destroyed once all protocol-defined procedures are completed. However, information collected from samples prior to the request for destruction, will be retained by Amgen.

Amgen is the exclusive owner of any data, discoveries, or derivative materials from the sample materials and is responsible for the destruction of the sample(s) at the request of the subject through the investigator, at the end of the storage period, or as appropriate (eg, the scientific rationale for experimentation with a certain sample type no longer justifies keeping the sample). If a commercial product is developed from this research project, Amgen owns the commercial product. The subject has no commercial rights to such product and has no commercial rights to the data, information, discoveries, or derivative materials gained or produced from the sample. See [Section 11.3](#) for subject confidentiality.

8. WITHDRAWAL FROM TREATMENT, PROCEDURES, AND STUDY

8.1 Subjects' Decision to Withdraw

Subjects have the right to withdraw from the study at any time and for any reason without prejudice to their future medical care by the physician or at the institution.

Subjects (or a legally acceptable representative) can decline to continue receiving investigational product and/or other protocol required therapies or procedures at any

time during the study but continue participation in the study. If this occurs, the investigator is to discuss with the subject the appropriate processes for discontinuation from investigational product or other protocol required therapies and must discuss with the subject the options for continuation of the Schedule of Assessments ([Table 5.](#)) and collection of data, including endpoints and adverse events. The Investigator must document the change to the Schedule of Assessments ([Table 5.](#)) and the level of follow-up that is agreed to by the subject (eg, in person, by telephone/mail, through family/friends, in correspondence/communication with other physicians, from review of the medical records).

Withdrawal of consent for a study means that the subject does not wish to receive further protocol-required therapies or procedures, and the subject does not wish to or is unable to continue further study participation. Subject data up to withdrawal of consent will be included in the analysis of the study, and where permitted, publicly available data can be included after withdrawal of consent. The investigator is to discuss with the subject appropriate procedures for withdrawal from the study.

8.2 Investigator or Sponsor Decision to Withdraw or Terminate Subjects' Participation Prior to Study Completion

The investigator and/or Amgen can decide to withdraw subjects from investigational product and/or other protocol required therapies, protocol procedures, or the study as a whole at any time prior to study completion.

Subjects may be eligible for continued treatment with Amgen investigational product(s) and/or other protocol required therapies by a separate protocol or as provided for by the local country's regulatory mechanism, based on parameters consistent with [Section 12.1.](#)

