6.7 Excluded Treatments, Medical Device Use, and/or Procedures During Study Period

The following medications and/or therapies should not be administered within the timeframes specified prior to enrollment or during the study (unless otherwise specified below):

- Treatment with immune modulators including, but not limited to, immunosuppressive dose of corticosteroid (>10 mg/day prednisone or equivalent), cyclosporine, and tacrolimus
- Anti-tumor therapy (chemotherapy, antibody therapy, molecular targeted therapy, or investigational agent); concurrent use of bisphosphonates or denosumab for bone loss are permitted
- Treatment with medications known to cause QTc interval prolongation unless approved by the Amgen Medical Team
- Concurrent use of warfarin, factor Xa inhibitors, and direct thrombin inhibitors unless agreed upon by Amgen and investigator (eg, use of agents such as low-dose aspirin and low-dose warfarin may be allowed)
- Any live vaccine therapies used for the prevention of infectious disease
- Any surgery or radiotherapy unless agree upon by Amgen and investigator

There are no prohibited therapies and procedures during the post-treatment follow-up.

- 7. STUDY PROCEDURES
- 7.1 Schedule of Assessments Dose Exploration and Dose Expansion

Approved

Table 5. Schedule of Assessments – Dose Exploration and Dose Expansion

Cycle	Treatment					EOT ⁽²¹⁾	EOS ⁽²¹⁾
	V and Beyond						
Weeks	Q3W		Q6W	Q9W			
Days							
Hours (relative to start of dosing)	Pre-dose	0	EOI	Pre-dose	Pre-dose		
GENERAL AND SAFETY ASSESSMENT							
Informed consent							
Clinical evaluation ⁽¹⁾	x					x	X
Vital signs ⁽²⁾	x		x			x	X
12-lead ECG ⁽³⁾				x3		x3	x3
Echocardiogram ⁽⁴⁾							
Peripheral Neuropathy Assessment ⁽⁵⁾				x		x	X
Prior/concomitant medication review							
Adverse events review							
LABORATORY ASSESSMENTS AND DOSING							
AMG 224 dosing ⁽⁶⁾		x					
AMG 224 PK ^{(7) (9)}	x					x	x
DM1 PK ^{(8) (9)}							
Anti-AMG 224 antibody collection (Immunogenicity)					x	x	x
Safety lab tests ⁽¹⁰⁾	x					x	x
Pregnancy test ⁽¹¹⁾					x	x	x
Hepatitis serology ⁽¹²⁾							
SPEP/UPEP/Immunofixation ⁽¹³⁾	x					x	x
SFLC ⁽¹⁴⁾	x					x	x
Quantitative Ig ⁽¹⁵⁾							
Beta-2 microglobulin							
Bone marrow, FISH ⁽¹⁶⁾							
Biomarker Bone Marrow Biopsy	<<						>>
Biomarker Bone Marrow Aspirate	<<						>>
Biomarker Blood Sample Collection ⁽¹⁷⁾							
Plasma				x		x	x
Serum				x		x	x
Cell Pellet				x		x	x
IMAGING ASSESSMENTS							
Plasmacytoma ⁽¹⁹⁾							
Skeletal survey ⁽²⁰⁾					x		

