8.3 Reasons for Removal From Treatment or Study

8.3.1 Reasons for Removal From Treatment

Reasons for removal from the investigational product include any of the following:

- subject request
- safety concern (eg, due to an adverse event)
- ineligibility determined
- protocol deviation
- non-compliance (eg, procedural or dosing as defined in [Section 6.2.1.1](#))
- requirement for alternative therapy
- pregnancy

- decision by Amgen (other than subject request, safety concern, or lost to follow-up)
- decision by investigator (other than subject request, safety concern, or lost to follow-up)
- death
- lost to follow-up
- Confirmed Disease Progression per IMWG ([Appendix D](#))

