^a Patients with measurable disease in both serum (SPEP) and urine (UPEP) at study entry are required to meet response criteria in both UPEP and SPEP in order to qualify for a MR or better. Conversely, it should be noted that criteria for PD only needs to be met, and confirmed, in one parameter.

^b **All response categories (CR, sCR, VGPR, PR) require 2 consecutive assessments** made at any time before the institution of any new therapy, as well as no known evidence of progressive or new bone lesions if radiographic studies were performed. Radiographic studies are not required to satisfy these response requirements. Bone marrow, plasmacytoma, and skeletal survey assessments are not required to be confirmed by repeat testing. SD requires a duration of ≥ 6 weeks.

^c Presence/absence of clonal cells is based upon the κ/λ ratio. An abnormal κ/λ ratio by immunohistochemistry and/or immunofluorescence requires a minimum of 100 plasma cells for analysis. An abnormal ratio reflecting presence of an abnormal clone is κ/λ of $> 4:1$ or $< 1:2$.

^d **Determination of PD while on study requires 2 consecutive assessments** made at any time before classification of PD and/or the institution of new therapy. Serum M-component increases of ≥ 1 g/dL from nadir are sufficient to define progression if nadir M-component is ≥ 5 g/dL.

^e Plasmacytomas: A definite increase in the size is defined as a $\geq 50\%$ increase as measured serially by the sum of the products of the cross-diameters of the measurable lesion. A plasmacytoma is considered measurable if the longest diameter is at least 1 cm and the product of the cross diameters is at least 1 cm². Plasmacytomas of lesser size will be considered non-measurable.

^f The requirement for bi-directional measurements applies only to plasmacytomas.

^g The plasmacytoma specifications for PD are based on interpretation of the IMWG-URC and practical considerations for study execution.

Approved

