4.2 Subgroups

Biomarker data may be incorporated in additional exploratory subgroup or multivariate analyses. The analyses of biomarkers may be performed after collection of all samples

during the conduct of the study and therefore may be reported after the primary analysis of efficacy endpoints.

5. Definitions

Age at Enrollment

Subject age at enrollment will be determined using the age in years reported in the clinical database.

AUC_{0-3 week} = AUC_{0-504 hrs}

It is defined as the area under the concentration-time curve from time 0 to 504 hours.

Baseline

Unless otherwise specified the baseline value for parameters/assessments scheduled to be performed on the same day as the first administration of AMG 224 (Q3W), is the last value measured before the first administration of AMG 224 on that day. For parameters/assessments not scheduled to be performed (or scheduled but not performed) on the same day as the first administration of AMG 224, the baseline value is the value from the screening period measured closest to the day of first administration of AMG 224. In the event that multiple assessments are done on the same day as the first administration of AMG 224 and there is no time associated with the assessments, the value associated with the last clinically planned event before the first administration of AMG 224 will be used as the baseline value.

For baseline ECG, three triplicate ECGs to be collected ≥ 30 minutes apart, with each ECG in triplicate approximately 30 seconds apart (3 set collected predose on day 1 with total of 9 ECGs) planned to be taken predose. Mean value will be calculated and used in the analysis. The mean of the values within a triplicate should be calculated before taking the mean of the triplicate averages. Where an ECG is missing within a triplicate, all available data will be averaged for that time point.

Best Overall Response

Best overall response for a subject is the best observed post baseline disease response per the International Myeloma Working Group Uniform Response Criteria for Multiple Myeloma (IMWG-URC).

Best Overall Response/Progression CRF will be employed to determine the response.

Every effort should be made to document the objective progression even after discontinuation of treatment.

Body Mass Index (BMI)

Body Mass Index should be calculated using the following formula

$$\text{BMI (kg/m}^2\text{)} = \text{weight (kg)} / [\text{height (cm)} / 100]^2$$

Change From Baseline

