Any subject meeting the criteria for Hy's Law case (ie, severe drug-induced liver injury) will be considered a DLT. A Hy's Law case is defined as: AST or ALT values of \geq 3x ULN AND with serum total bilirubin level (TBL) of $>$ 2x ULN without signs of cholestasis and with no other clear alternative reason to explain the observed liver-related laboratory abnormalities.

Duration of Response (DOR)

Duration of response is defined as the number of days between the date of the first observation indicating an objective response as PR (or better) through to the subsequent date of disease progression as classified by per the International Myeloma Working Group Uniform Response Criteria for Multiple Myeloma or death or where applicable date of censoring [date of first progressive disease assessment or death or date of censoring – date of the first observation indicating PR (or better) as an objective response +1]. Subjects who respond (PR or better) and have not progressed while on study or not died will be censored at the date of assessment of the last evaluable response as documented on International Myeloma Working Group Uniform Response Criteria for Multiple Myeloma CRF. Subjects who do not achieve an objective response will be excluded from the analysis of duration of response.

End of IP Administration Date

End of IP Admin for each subject is defined as the date the decision was made to end IP as recorded on the End of Investigational Product Administration CRF page.

End of Study (Individual Subject)

End of study for each subject is defined as the date the subject last completed a protocol-specified procedure. The date will be recorded on the End of Study CRF page.

Enrollment Date

Enrollment Date is defined as the date collected on 'Subject Enrollment' CRF.

Fridericia-corrected QT Interval (QTcF)

The Fridericia correction will be calculated from the investigator reported QT (msec) and RR interval (msec), as follows: $QTcF = QT / (RR/1000)^{0.33}$

Use above definition for derivation only if QTcF is not collected in the CRF.

Investigational Product

The term 'investigational product' is used in reference to AMG 224.

Last Investigational Product Dose Date

The last IP dose date for each subject is defined as the latest date IP is administered.

Measurable Plasmacytoma

A plasmacytoma is considered measurable if the longest diameter is at least 1 cm and the product of the cross diameters is at least 1 cm².

Maximum Tolerated Dose (MTD)

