Time to response is calculated as the number of days from the first administration of AMG 224 to the first response as per IMWG-URC. It is calculated for subjects with PR or better.

Treatment-Emergent Adverse Event (TEAE)

A treatment-emergent adverse event is any adverse event starting on or after the first administration of investigational product, as determined by the flag indicating if the adverse event started prior to the first dose on the Events CRF, and up to and including 37 days after the end of investigational product. The severity of each adverse event will be graded using the CTCAE version 4.0. Adverse events will be coded using MedDRA.

Treatment-Related AE

A treatment-related AE is any treatment-emergent AE that per investigator review has a reasonable possibility of being caused by the investigational product.

Time to Progression (TTP)

Time to progression is calculated as the number of days from the first administration of AMG 224 to the first objective assessment of disease progression as per IMWG-URC or deaths or if applicable date of censoring (date of progressive disease / death or censoring – date of first administration of AMG 224 +1).

If a subject's disease has not progressed and the subject is alive, time to progression will be censored at the last date they are known to be progression-free (ie, date of assessment of the last evaluable response as documented on International Myeloma Working Group Uniform Response Criteria for Multiple Myeloma CRF).

If a subject has no evaluation related to assessment of response criteria of Multiple Myeloma (IMWG-URC) in the study, time of response will be censored at the date of the first administration of AMG 224.

Subjects who withdraw consent to participate in the study prior to disease progression will be censored at their last evaluable assessment of response documented on IMWG-URC for Multiple Myeloma CRF.

6. Analysis Sets

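### TTP, DOR and the 6-month progression-free proportion have no cut at new anti-myeloma therapy, so assessments made on the next drug can count toward AMG 224

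*Protocol*

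**What the plan says.** **Assessments after AMG 224 stops.** Protocol 7.2.24 and Table 5 schedule SPEP, UPEP and SFLC at the end-of-study (EOS) visit, 30 to 37 days after the last dose. Protocol 8.1 covers subjects who decline further product but remain on study. The investigator must discuss with them the options for continuing the schedule and the "collection of data, including endpoints and adverse events". For best overall response, SAP Section 5 adds: "Every effort should be made to document the objective progression even after discontinuation of treatment".

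**New therapy in that period.** Protocol 6.7 states: "There are no prohibited therapies and procedures during the post-treatment follow-up". Protocol 8.3.1 lists "requirement for alternative therapy" as a reason to leave treatment. Protocol 8.3.2 does not list it as a reason to leave the study.

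**Censoring.** SAP Section 5 counts progression or death as the event for both endpoints.
- TTP: for a subject alive without progression, "time to progression will be censored at the last date they are known to be progression-free". Separate rules cover subjects with no evaluation and subjects who withdraw consent.
- DOR: "Subjects who respond (PR or better) and have not progressed while on study or not died will be censored at the date of assessment"; the assessment meant is the most recent evaluable one.

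SAP 9.5.2.3 reports the proportion progression-free at 6 months with an exact 80% interval. None of these places mentions new anti-myeloma therapy.

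**Response criteria.** In the footnotes to Protocol Appendix D, CR, sCR, VGPR and PR need two consecutive assessments "made at any time before the institution of any new therapy". Progression needs two consecutive assessments "made at any time before classification of PD and/or the institution of new therapy".

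**The concern.** The time-to-event rules and the criteria they rely on do not meet. Appendix D uses the start of new therapy to limit which assessments can confirm a response or a progression, but it sets no censoring date. The SAP sets censoring dates without reference to new therapy. Take a subject who stops AMG 224 without progression, starts another drug and is found progression-free at EOS. Applied as written, the SAP rule places that subject's last progression-free date on the other drug.

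The trial has no control group, so nothing in its own results would show the effect. Two programmers could also derive different TTP and DOR values from the same records, depending on whether each carries the Appendix D limit over to the censoring date.

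**Working it through.** **The plan's own figures.** The documents give no assumption for TTP, DOR or 6-month status, so there is no planned value to reproduce for these endpoints. The only planned efficacy figure, the exact 80% interval for 4/20 responders, does reproduce: 9.0% to 36.1%, against 9% to 36% stated. It does not bear on this point.

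**Size of the effect: inputs, all assumed.**
- True median TTP on AMG 224, *m*: 3 or 6 months.
- Probability *s* of stopping without progression by 6 months (absent progression): 10% or 30%. All who stop start new therapy at once.
- Hazard ratio *h* on the new drug: 0.3 or 0.6.
- Follow-up after stopping, *w*: 37 days (37/30.44 = 1.22 months, the EOS path), or continued past 6 months (the 8.1 path).
- Stopping is independent of prognosis.

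**Formulas.** Progression hazard λ = ln 2 / *m*; stopping hazard μ = −ln(1 − *s*)/6. The true 6-month rate is exp(−6λ), which is 25% for *m* = 3 and 50% for *m* = 6. Without a cut, those at risk at time *t* are
- on AMG 224: A(t) = exp(−(λ+μ)t);
- on the new drug and still followed: B(t) = ∫ μ exp(−(λ+μ)u) exp(−hλ(t−u)) du, for u from max(0, t−w) to t.

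The Kaplan-Meier curve then follows the hazard λ(A + hB)/(A + B), and the 6-month rate is exp(−∫₀⁶ hazard dt).

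| True 6-month rate | *s* | *h* | Uncut, EOS path | Uncut, follow-up continued |
|---|---|---|---|---|
| 25% | 10% | 0.3 | 25.5% | 26.8% |
| 25% | 10% | 0.6 | 25.3% | 25.9% |
| 25% | 30% | 0.3 | 26.7% | 30.5% |
| 25% | 30% | 0.6 | 25.9% | 27.7% |
| 50% | 10% | 0.3 | 50.5% | 51.5% |
| 50% | 10% | 0.6 | 50.3% | 50.8% |
| 50% | 30% | 0.3 | 51.6% | 54.6% |
| 50% | 30% | 0.6 | 50.9% | 52.4% |

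Simulation of 400,000 subjects per case agrees within 0.2 points. It gives a rise of 0.3 to 1.9 points on the EOS path and 0.7 to 5.5 points with continued follow-up. The uncut median on the EOS path is 3.03 to 3.14 months (true 3) or 6.05 to 6.28 months (true 6). Censoring at new therapy returns the true values to within simulation error, because stopping was assumed independent of prognosis.

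A second set of assumed inputs used a median of 3 to 6 months, 19% to 26% stopping without progression by 6 months, new therapy 14 days later and a hazard ratio of 0.25 to 0.5. It gives a rise of 0.6 to 1.3 points on the EOS path (for example 35.2% to 36.1%) and 2.6 to 6.8 points with continued follow-up.

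**Direction.** The formula shows that the sign depends on *h*. Below 1 the curve is too high, at 1 it is unaffected, and above 1 it is too low.

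**The 6-month proportion.** This is a binomial proportion, not a Kaplan-Meier estimate, and its bias was not calculated. One subject of 20 moves it by 1/20 = 5 points.

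**The case against.** **Appendix D may already do the work.** TTP and DOR follow the IMWG criteria and censor at the last evaluable response. If a value taken after a switch cannot support a response, it can be argued that it is not evaluable, so a responder's DOR would be censored before the switch. This is a fair reading for responders. But the footnote covers CR, sCR, VGPR and PR; it says nothing equivalent for minor response or stable disease, which matter for TTP, and it fixes no censoring date. The argument does stand for best overall response, which needs no change.

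**Few subjects are exposed.** Section 8.1 concerns subjects who decline product and requires only a discussion of options. Study participation normally ends at EOS (Protocol 3.5.2), Table 5 has no later column, and a treatment-related delay of more than 3 weeks removes the subject from the study (Protocol 6.2.1.5). This stands. A reader might infer that subjects stopping for toxicity are routinely followed for months on their next drug; the documents do not support that, so the larger figures above describe an exception.

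**The effect is small beside the sampling error.** The exact 80% interval for 7/20 runs from 21% to 52%, so a shift of 1 or 2 points would not change a descriptive reading. This also stands.

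**Counting events regardless of later therapy is a legitimate choice.** It is, but the SAP does not state that choice, and Appendix D points the other way.

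**Conclusion.** The gap is real and worth closing, as an improvement to secondary, descriptive endpoints. As written, the rules can count progression-free time on another drug toward AMG 224, and they can equally count progression or death on that drug against it. Only subjects who start new therapy before documented progression and are assessed, or die, afterwards are affected.

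Under the assumed inputs the Kaplan-Meier 6-month rate shifts by about 0.3 to 2 points on the scheduled EOS path. It shifts by more (up to 5.5 or 6.8 points in the two sets of inputs) only if follow-up under 8.1 continues for everyone who stops without progression. These sizes rest on exponential times, stopping unrelated to prognosis, and a next drug that works better than AMG 224.

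Two stronger readings are tempting and not supported:
- **That the endpoints are necessarily biased upward.** The direction depends on the next drug, because its failures also count as events.
- **That the inflation reaches 6 to 11 points.** That requires rejecting progression after new therapy under Appendix D while still accepting non-progression after new therapy. No section prescribes that asymmetry. If post-switch assessments are excluded for both, the bias goes away.

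**What to change.** In SAP Section 5 (TTP and DOR) and 9.5.2.3:
- use only assessments made before the first new anti-myeloma therapy;
- censor subjects who start such therapy without prior progression or death at their last evaluable assessment before it, and state how they are classified in the 6-month proportion;
- report how many subjects are censored for this reason;
- keep the uncut analysis as a sensitivity.

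Leave best overall response as it is.

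Protocol 6.5 already collects the start dates of concomitant therapy through EOS, so the scheduled path needs only a derivation. Where response is assessed later under 8.1, the start date of new therapy has to be collected for as long as those assessments continue.

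The cost is a few sentences in the SAP, one derived date and a small addition to data collection. No visit, treatment or sample size changes. The downside is that censoring at a switch may be informative, since subjects who move to another drug may differ in prognosis. The reported count and the uncut sensitivity analysis let the reader judge that.
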